The Frederick W. Thompson Anxiety Disorders Centre has experienced significant demand for services related to the treatment of Obsessive Compulsive Disorder (OCD), resulting in a significant wait time for service. Although Cognitive Behavior Therapy (CBT) is the most efficacious treatment intervention for OCD (McKay et al., 2015), there is a growing literature indicating the mindfulness based approaches can be beneficial in terms of managing acute mood and anxiety symptoms as well as reducing relapse risk following treatment (e.g., Huijbers et al., 2016). The National Institute for Health and Care Excellence (NICE) guidelines provide a framework for health professionals who provide integrated, comprehensive treatments for the management of mood and anxiety disorders. These guidelines suggest that clinicians provide clients with accessible, low intensity, low risk interventions as they await treatment. It may be that having clients engage in low intensity interventions while they wait for CBT treatment can prevent symptom exacerbation and improve their motivation to engage in subsequent hospital based treatments. Although past research has demonstrated the benefits of engaging in guided mindfulness meditation practice in terms of psychological symptom improvement, it is unclear whether self-guided meditation practice incorporating biofeedback could promote symptom alleviation for individuals experiencing OCD. The goal of this study is to examine the potential benefits of using a consumer grade EEG-based biofeedback device that allows clients to engage in home based mindfulness meditation practices while they are waiting to receive clinical services. Specifically, this study will investigate the effects of meditation home practice on symptom alleviation, as related to specific OCD related cognitive processes. Patients who are waiting to receive clinical services will engage in an initial clinical assessment prior to being offered service, which is standard clinical practice. Following a clinical assessment, the patient will be offered the opportunity to participate in the current study - regardless of their decision to participate, they will still receive treatment recommendations and be considered for an upcoming clinical treatment service as usual, as determined by the assessor. If they choose to be involved in this study, they will be randomized to one of two groups: either an eight week waitlist control condition, or an eight week mindfulness treatment condition. Participants in the mindfulness condition will receive a commercially available wireless EEG headset and a software package that provides guided meditation practices with auditory feedback. Participants will attend three sessions during the eight week protocol – each session involves completing a self-report questionnaire package (evaluating OCD symptoms, mindfulness and thought control strategies) and they will complete a brief open monitoring meditation practice using the Muse EEG headset. Participants in the meditation condition will engage in regular mindfulness practice during each week, and complete a brief online survey regarding their experience during the mindfulness practice, once per week.

1 Specific Aims

This study will examine the potential benefits of engaging in mindfulness practices, for patients experiencing OCD who are waiting for clinical services to be offered. Patients will be offered a low intensity, low risk mindfulness intervention that is delivered by a consumer grade wireless EEG biofeedback device that provides guided mindfulness practices with biofeedback. Specifically, we will examine whether engaging in guided mindfulness meditation home practices can promote symptom alleviation, as related to variables which may influence treatment response (mindfulness, OCD beliefs, thought control strategies). If this intervention is found to be helpful, patients who are waiting for clinical services to be offered may experience symptom alleviation, which may, in turn, help them to optimally benefit from subsequent services offered by our clinic. If we determine that this intervention is efficacious, this approach could be further disseminated to other hospital based clinical programs, particularly those services in which wait times may be excessive.

2 Background and Significance

2.1 Background

Obsessive Compulsive Disorder (OCD) is a chronic and debilitating disorder known to have reported lifetime prevalence in the range of 2% (Kessler et al., 2005). OCD is most commonly treated with Cognitive Behavioral Therapy (CBT) and/or pharmacotherapy. Although Cognitive Behavior Therapy (CBT) is the most efficacious treatment intervention for OCD (McKay et al., 2015), there is often a substantial wait time for patients awaiting CBT services. The National Institute for Health and Care Excellence (NICE) guidelines provide a framework for health professionals who provide integrated, comprehensive treatments for the management of mood and anxiety disorders. These guidelines suggest that it can be beneficial for patients to be provided with easily accessible, low intensity, low risk interventions as they await treatment. It may be that engaging in low intensity interventions can prevent symptom exacerbation and improve patients' motivation to engage in subsequent hospital based treatments.

The existing research literature indicates that mindfulness based approaches can be beneficial in terms of managing mood and anxiety symptoms as well as reducing relapse risk following treatment (e.g., Huijbers et al., 2016). There is a substantial treatment efficacy literature indicating that engaging in mindfulness strategies can lead to psychological symptom alleviation (Segal et al., 2002; Brown & Ryan, 2003; Keng, Smoski & Robins, 2011) in a broad range of clinical populations (Baer, 2003; Chisea & Serretti, 2010; Strauss, Cavanagh, Oliver, & Pettman, 2014), as well as having a prophylactic effect in terms of reducing depression relapse risk following CBT treatment (e.g., Teasdale et al., 2000; Kuyken et al, 2016). For patients who have been diagnosed with an anxiety or mood disorder, mindfulness interventions are associated with effect sizes (Hedges' g) of 0.97 and 0.95 for improving anxiety and mood symptoms, respectively (Hofmann, Sawyer, Witt & Oh, 2010). Further, there is an emerging literature examining the potential benefits of utilizing mindfulness techniques for individuals experiencing OCD (e.g., Strauss, Rosten, Hayward, Lea, Forrester & Jones, 2015). These individuals experience difficulties with managing intrusive, disturbing, obsessive thoughts that produce considerable distress and anxiety (Abramowitz, Taylor & McKay, 2009). As a result, they engage in strategies that promote experiential avoidance, involving compulsive, problematic thought control strategies in order to neutralize their obsessive thoughts (e.g., Abramowitz et al., 2009). Essentially, these thought control strategies run counter to mindfulness strategies which promote experiential awareness. Considering this, there are several reasons why engaging in mindfulness strategies may promote OCD symptom alleviation. By cultivating improved experiential awareness, patients may become capable of adopting a more accepting approach to managing their problematic obsessive thoughts, feelings, and physical sensations, thereby developing a "decentered", non-reactive attitude towards these experiences (Bieling et al., 2012). To date, there have been no studies that have examined whether engaging in weekly guided mindfulness meditation practices (using an EEG based biofeedback device) may be effective for individuals experiencing OCD. Therefore, this study sets out to examine the potential benefits of offering an easily accessible, low intensity intervention in order to promote OCD symptom alleviation, as related to OCD beliefs, mindfulness, mind wandering, motivation, and engagement in thought control strategies.

2.2 Significance

As a result of an increasing demand for specialized mental health services, wait lists for treatment are more the norm than the exception. It is plausible to assume that providing clients with an EEG based biofeedback device that provides guided meditation practices will impact on symptom alleviation while clients are awaiting treatment. In addition, this research protocol has the potential to provide us with additional valuable information about the nature and course of OCD, providing insight into mechanisms underlying treatment response, thereby adding to our understanding of this disorder and its' treatment. By learning more about factors that are involved in the disorders' presentations such as clients' use of thought control strategies, OCD related beliefs, the quality of their mindfulness practice, and their motivation to engage in CBT in the future, we can improve our

understanding of the mechanisms underlying the disorder and help improve the quality of treatment for these individuals.

It is hypothesized that clients participating in the meditation group (in comparison to the wait list control group) will see greater reductions in self-reported measures of symptom severity and improvement in their use of problematic thought control strategies, as well as their readiness to engage in subsequent treatment. If this study can demonstrate that engaging in eight sessions of guided mindfulness practice can provide benefits for those suffering with OCD, then it provides another route by which patients can experience symptom improvement while waiting for a more structured, evidence-based CBT treatment. If this intervention is found to be helpful, patients who are waiting for clinical services to be offered may experience symptom alleviation, which may, in turn, help them to optimally benefit from subsequent services offered by our clinic. Further, if we determine that this intervention is efficacious, this approach could be further disseminated to other hospital based clinical programs, particularly those services in which wait times may be excessive.

3 **Research Design and Methods**

3.1 Research Design and Methods

Recruitment and Procedure

Patients referred for consultation and treatment services at the Frederick W. Thomspon Anxiety Disorder Centre will be eligible for participation. Patients presenting with OCD who are currently awaiting services at the Centre will be recruited for participation in this study. However, those with active substance abuse/dependence, suspected organic pathology as listed on the referral form, recent suicide attempt/active suicideality, active bipolar disorder, psychotic disorder or post-traumatic stress disorder will be excluded from participation.

Outcome measures will assess OCD symptom severity, OCD beliefs, the quality of their mindfulness practice, OCD thought control strategies, and whether they experience spontaneous or deliberate "Mind Wandering" during their mindfulness practice. OCD symptom measures will include the self-report Yale-Brown Obsessive Compulsive Scale (YBOCS), and the Obsessive Compulsive Inventory-Revised (OCI-R). OCD beliefs will be measured by the Obsessive Beliefs Questionnaire (OBQ-44). The Five Factor Mindfulness Questionnaire (FFMQ) will be used to measure the quality of participants' mindfulness practice. The Acceptance and Action Questionnaire (AAQ-II) will be used to measure psychological flexibility. The Thought Control Questionnaire (TCQ) will measure participants' tendency to engage in efforts to control intrusive thoughts. The Mind Wandering Scale (MW) will be used to determine the extent to which participants experienced spontaneous or deliberate mind wandering during their mindfulness practice. Motivation and readiness to engage in subsequent CBT treatment will be measured using the Readiness Ruler (RR). Daily practice data from the EEG headsets will be automatically uploaded to an encrypted server.

At baseline, mid treatment (session 4), and post intervention, participants will complete the YBOCS, OCI, OBQ, FFMQ, TCQ, AAQ, MW and MCQ. Once per week, participants in the mindfulness condition will complete the YBOCS, TCQ, and MW. This weekly data will be collected online using the "Survey Monkey" web portal.

Experimental Design

The study will be a randomized trial where subjects (N=100 Total, N=50 assigned to Group 1 (Mindfulness condition) or Group 2 (Control condition) will be randomly assigned to receive either 1) an eight week meditation program involving use of an EEG-based biofeedback device, or 2) wait list as per usual. The experimental design is a 2 (treatment condition) by 3 (assessment phase: baseline (week 0), mid treatment (week 4), and post-treatment (week 8)) repeated measures factorial design. Randomization will be completed

by staff separate from the research team using numerical randomization for consecutive referrals.

Data Analyses

A repeated measures multivariate analysis of variance (MANOVA) will be conducted with the two groups (guided mindfulness meditation or control wait list group) as the between-group variable and OCD symptom scores as the dependent variables. A mediation analysis will examine whether obsessive beliefs, engagement in thought control strategies, psychological flexibility, and mind wandering mediates treatment related changes in OCD symptom scores (YBOCS, OCI). A Latent Difference Score (LDS) analysis will examine longitudinal temporal relationships between OCD symptoms and each of the above mentioned variables. Daily practice data from the EEG headsets will be automatically uploaded to an encrypted server. These data will be made anonymous from the start of the study; subjects will be identified using their subject I.D. EEG data will be measured in latency windows selected according to prior research and determined from visual inspection of the waveforms. Analyses of variance (ANOVAs) will be computed on peak and mean amplitude using group as a between-subjects factor and session (pre or post), task condition, and electrode as within-subject factors.

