Most people experience unpleasant and/or unwanted thoughts (in verbal and/or picture form) which can be difficult to control. We are interested in the techniques that you *generally* use to control such thoughts. Below are a number of things that people do to control these thoughts. Please read each statement carefully, and indicate how often you use each technique by *circling* the appropriate number. There are **no right or wrong answers** to these questions. Do not spend too much time thinking about each one.

	Never	Sometimes	Often	Almost always
I call to mind positive images instead	1	2	3	4
I tell myself not to be so stupid	1	2	3	4
I focus on the thought	1	2	3	4
I replace the thought with a more trivial bad thought	1	2	3	4
I don't talk about the thought to anyone	1	2	3	4
I punish myself for thinking the thought	1	2	3	4
I dwell on other worries	1	2	3	4
I occupy myself with work instead	1	2	3	4
I challenge the thought's validity	1	2	3	4
I get angry at myself for having the thought	1	2	3	4
I avoid discussing the thought	1	2	3	4
I shout at myself for having the thought	1	2	3	4
I analyze the thought rationally	1	2	3	4
I slap or pinch myself to stop the thought	1	2	3	4
I think pleasant thoughts instead	1	2	3	4
I find out how my friends deal with these thoughts	1	2	3	4
I worry about more minor things instead	1	2	3	4
I do something that I enjoy	1	2	3	4
I try to reinterpret the thought	1	2	3	4
I think about something else	1	2	3	4
I think about the more minor problems I have	1	2	3	4
I try a different way of thinking about it	1	2	3	4
I think about past worries instead	1	2	3	4
I ask my friends if they have similar thoughts	1	2	3	4
I focus on different negative thoughts	1	2	3	4
I question the reasons for having the thought	1	2	3	4
I tell myself that something bad will happen if I think the thought	1	2	3	4
I talk to a friend about the thought	1	2	3	4
I keep myself busy	1	2	3	4

When I experience an unpleasant / unwanted thought:

Mind Wandering: Deliberate

For the following statements please select the answer that most accurately reflects your everyday mind wandering.

1. I allow my thoughts to wander on purpose.

Rarely						A Lot
1	2	3	4	5	6	7

2. I enjoy mind-wandering.

Rarely						A Lot
1	2	3	4	5	6	7

3. I find mind-wandering is a good way to cope with boredom.

Not At All True						Very True
1	2	3	4	5	6	7

4. I allow myself to get absorbed in pleasant fantasy.

Rarely						A Lot
1	2	3	4	5	6	7

Mind Wandering: Spontaneous

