For the following statements please select the answer that most accurately reflects your everyday mind wandering.

1. I find my thoughts wandering spontaneously.

Rarely						A Lot
1	2	3	4	5	6	7

2. When I mind-wander my thoughts tend to be pulled from topic to topic.

Rarely						A Lot
1	2	3	4	5	6	7

3. It feels like I don't have control over when my mind wanders.

Almost Never						Almost Always
1	2	3	4	5	6	7

4. I mind-wander even when I'm supposed to be doing something else.

Rarely						A Lot
1	2	3	4	5	6	7

AAQ-II

Below you will find a list of statements. Please rate how true each statement is for you by circling a number next to it. Use the scale below to make your choice.

Never true 1	,	Very seldom true 2	Seldom true 3	Sometimes true 4	Frequently true 5	A	lmost	always 6	true		Alway	/s true 7
	1.	It's OK if I remen	nber something	unpleasant		1	2	3	4	5	6	7
	2.	My painful exper live a life that I w		nories make it diffi	cult for me to	1	2	3	4	5	6	7
	3.	I'm afraid of my f	feelings.			1	2	3	4	5	6	7
	4.	I worry about not	t being able to c	ontrol my worries a	and feelings.	1	2	3	4	5	6	7
	5.	My painful memo	ories prevent m	e from having a ful	filling life.	1	2	3	4	5	6	7
	6.	I am in control of	f my life			1	2	3	4	5	6	7
	7.	Emotions cause	problems in my	ılife.		1	2	3	4	5	6	7
	8.	It seems like mo	st people are ha	andling their lives b	etter than I am.	1	2	3	4	5	6	7
	9.	Worries get in th	e way of my suc	ccess.		1	2	3	4	5	6	7
	10.	My thoughts and live my life	l feelings do not	get in the way of h	now I want to	1	2	3	4	5	6	7

Instructions: Please circle the line on the ruler below that you feel appropriately captures your desire to change and your feelings about being capable of change:

[figure not shown]
1. On a scale from **1** to **10**, how important is it to you to improve your obsessive/compulsive symptoms?

	ot at al oortant					newhat portant				Extremely Important
(
	1	2	3	4	5	6	7	8	9	10
(

[figure not shown]
2. On a scale from 1 to 10, how confident do you feel that you can succeed in improving your obsessive/compulsive symptoms?

No	ot at all				Son	newhat				Extremely
Cor	nfident				Сог	nfident				Confident
	1	2	3	4	5	6	7	8	9	10

3. On a scale from 1 to 10, how ready are you to make changes in your life in order to improve your obsessive/compulsive symptoms?

3. On a scale from 1 to 10, how motivated are you to engage in upcoming weekly Cognitive Behavior Therapy sessions for Obsessive Compulsive Disorder?

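### The plan defines the Mind Wandering Scale as wandering during mindfulness practice, but the appended forms ask about everyday wandering, so the mediation result would carry the wrong meaning

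*Combined protocol and SAP*

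**What the plan says.** Section 3.1 (Recruitment and Procedure) assigns the Mind Wandering Scale to one construct: "the extent to which participants experienced spontaneous or deliberate mind wandering during their mindfulness practice". Section 4 describes the scale in the same way. The outcome lists that open the description of measures in both sections also tie mind wandering to practice.

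Section 3.1 gives MW to participants at baseline, mid treatment and post intervention, and once a week to the mindfulness arm.

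Two MW forms are appended, one headed Deliberate and one headed Spontaneous, with four items each. Both carry the same instruction: "For the following statements please select the answer that most accurately reflects your everyday mind wandering".

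Data Analyses (Section 3.1) asks whether obsessive beliefs, thought control strategies, "psychological flexibility, and mind wandering mediates treatment related changes in OCD symptom scores". The LDS analysis then relates OCD symptoms to each of those variables over time. No scoring rule is given for MW.

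**The concern.** The construct in the plan and the construct on the form are different. How far attention drifts during meditation is a property of the practice. A tendency to daydream in daily life is a general habit. Either could change without the other.

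The distinction matters because of how the intervention is meant to work. Section 6 says that feedback is given when the application judges that attention has drifted during a session, and Section 2.2 lists insight into the mechanisms of treatment response among the study's purposes. Someone who takes the definition from Sections 3.1 and 4 would read a significant indirect effect through MW as support for that mechanism, and a null one as evidence against it. The score supports neither reading.

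A second, smaller gap lies in the same variable. The forms are two scales with different content, and Data Analyses names only mind wandering, so the variable that enters the models is not determined.

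**Working it through.** No formula applies, and the plan gives no figure to reproduce. The check sets the texts side by side.

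1. **Plan's definition.** There are two descriptions of the scale (Sections 3.1 and 4), and 2 of 2 are specific to practice.
2. **Form instructions.** There are two forms, and 2 of 2 say everyday. Neither gives a recall period.
3. **Items.** There are 4 deliberate + 4 spontaneous = 8 items, and 0 of 8 mention meditation or practice. One deliberate item reads "I find mind-wandering is a good way to cope with boredom". One spontaneous item reads "I mind-wander even when I'm supposed to be doing something else". Both describe habits in general.
4. **Is this only loose wording?** The same appendix shows what a practice-anchored form looks like: the Mindfulness Practice Questionnaire (MPQ) asks the respondent to consider the practices of the past week. The MW forms have nothing comparable.
5. **Role in the analysis.** Mind wandering is one of four named mediators (obsessive beliefs, thought control strategies, psychological flexibility, mind wandering), each examined against two symptom scores (YBOCS, OCI). It also enters the LDS analysis. No other instrument is assigned to it, so the mediator score will be everyday mind wandering whatever the plan calls it.
6. **Where the conflict lies.** The mediation sentence says mind wandering without qualification, as does the statement of purpose in Section 2.1. The everyday form fits both. The conflict is between the form and the definition of the scale in Sections 3.1 and 4, and the mediation result takes its meaning from that definition.
7. **Can the everyday score be used?** Yes. It can be answered by both arms at weeks 0, 4 and 8, so a between-arm mediation model remains feasible.
8. **One variable or two?** The deliberate items describe wandering that is chosen or enjoyed. The spontaneous items describe wandering that arises unbidden or escapes control. Section 3.1 itself distinguishes the two. Separate scores take the mediators from 4 to 5 and the mediator-by-outcome pairs from 4 × 2 = 8 to 5 × 2 = 10.

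**The case against.** The best defence is that this is a slip in describing the scale. The mediation sentence does not say during practice, the everyday form suits a comparison of two arms, and the primary comparison does not depend on it. All of that is correct, and it makes the repair cheap. It does not make the slip harmless: the plan defines the scale in two places, both times as practice-specific, and a result would be interpreted under that definition.

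Four stronger readings are tempting, and the documents do not support them.

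- *Wandering during practice could not be measured at baseline or in the wait-list arm.* The opening summary says that participants do a short open-monitoring meditation with the headset at each of the three sessions. It turns to the meditation condition only in the next sentence, so this appears to cover both arms. The planned EEG analyses, with group as a between-subjects factor and session (pre or post) within subjects, agree. Whether the questionnaires come before or after that meditation is not stated, but the construct is not impossible.
- *No scheduled self-report touches attention in practice.* Section 4 lists the MPQ among the pre, mid and post measures. Its item 12 asks about awareness of, and reaction to, the mind having wandered. It does not ask how much wandering occurred, the visit schedule in Section 3.1 omits the MPQ, and it is not named as a mediator. The flat statement would still be wrong.
- *The two scales will be added and opposite changes will cancel.* Nothing in the plan says that they will be summed, and no expected direction is given for either.
- *The weekly survey only needs a practice-specific stem.* Items such as the one on boredom would fit such a stem poorly, and weekly scores would no longer be comparable with visit scores.

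**Conclusion.** The concern holds as a mismatch of construct. The plan's definition is practice-specific in 2 of 2 places, the forms are everyday in 2 of 2, and 0 of 8 items refer to practice. It affects the interpretation of one of four planned mediators and of the same variable in the LDS analysis. It does not affect the group comparison on YBOCS and OCI or the sample size, and it does not make the mediation model infeasible. It should be corrected before analysis because, followed as written, the plan attaches the wrong meaning to a planned result.

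This rests on the appended forms being the ones administered; the documents contain no other MW form. The case for separate scores rests on the content of the items and on the absence of a scoring rule, not on any evidence that the two scales move in opposite directions.

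**What to change.** - **Sections 3.1 and 4:** define MW as everyday mind wandering, deliberate and spontaneous, in the descriptions of the scale and in the outcome lists.
- **Data Analyses:** name the mediator as everyday mind wandering, and enter the deliberate and spontaneous four-item scores as two separate variables in the mediation and LDS models.
- **Interpretation:** state that MW supports no conclusion about mind wandering during practice.

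The cost is a few changed sentences and one more mediator. No form, visit or data collection changes. The downside is small: a fifth mediator adds two mediator-by-outcome pairs to the eight already implied.

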5.6 Benefits

The benefit of participating in this study involves the likelihood of improving significantly in both symptom measures as well as measures demonstrated to underlie treatment response in OCD.

6 Intervention:

MUSE Guided Meditation Practices: The guided meditation intervention will be administered using

Interaxxon's Muse device. Muse is a wireless EEG headset with an accompanying mobile device software application. The headset has 4 dry sensors (2 mastoid and 2 forehead sensors) and fits over the ears and extends at an angle over the middle of the forehead when properly fitted. Data are sampled at 220 Hz and referenced to Fpz channel. The data is communicated wirelessly to the mobile device application.

Participants are asked to engage in a daily mindfulness practice, with each practice lasting for a minimum of 20 minutes, once per day. Participants may engage in additional practices if they feel motivated to do so. To provide high-fidelity neurofeedback during meditation practice, Interaxxon has established an algorithm that involves a combination of frequency bands that have been associated with meditative states (Kerr, Sacchet, Lazar, Moore, & Jones, 2013). When the application determines that the participant's "mind wandered", biofeedback is provided in order to assist the participant with refocussing their attention on their meditation practice. The software application provides a guided pre-session calibration to customize neurofeedback to match participant experience prior to each training session. Calibration involves two brief exercises: in the first exercise, participants are asked to perform a word association task to simulate a period of mind-wandering. In the second exercise, participants are asked to relax and clear their minds as a brief induction of a focused attention state. These two calibration conditions are then entered into a machine learning algorithm to generate a session-specific signature of concentration and distraction customized to the participant. Calibration lasted 1 minute. Following calibration, guided meditation instructions were delivered through the paired smartphone/iPad, directing participants attention towards sensations of the breath, body, and/or cognition. Neurofeedback is delivered through auditory cues of wind and storm sounds, which increase in intensity with greater estimated distraction, and subsided towards calm with greater estimated stability of attention.

7 Costs and Payments

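### The planned EEG measures (latency windows, peak and mean amplitude, a task-condition factor) do not fit the meditation recordings described for both arms, and nothing stops windows being set where the arms differ

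*Combined protocol and SAP*

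**What the plan says.** All of this is in the combined protocol and SAP.

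- **Measurement** (Section 3.1, Data Analyses): "EEG data will be measured in latency windows selected according to prior research and determined from visual inspection of the waveforms". No study, component, interval or time-locking event is named.
- **Model** (same paragraph): ANOVAs on "peak and mean amplitude using group as a between-subjects factor and session (pre or post), task condition, and electrode as within-subject factors". The levels of task condition are not given.
- **EEG in both arms** (opening summary): at each of three study sessions participants fill in questionnaires and "they will complete a brief open monitoring meditation practice using the Muse EEG headset".
- **Home EEG**: the summary says "Participants in the mindfulness condition will receive a commercially available wireless EEG headset", and Section 3.1 adds "Daily practice data from the EEG headsets will be automatically uploaded to an encrypted server".
- **Device** (Section 6, Intervention): two short calibration exercises come before each training session. One is word association, the other a settling exercise. "These two calibration conditions are then entered into a machine learning algorithm". During practice, when the application judges that attention has drifted, "biofeedback is provided in order to assist the participant with refocussing their attention on their meditation practice". The sound is graded: "Neurofeedback is delivered through auditory cues of wind and storm sounds, which increase in intensity with greater estimated distraction".
- **Masking**: EEG data are coded by subject ID, and staff outside the research team randomize. Neither provision masks the person who sets the windows.

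**The concern.** The plan never uses the term event-related, but latency windows, waveforms and peak amplitude are the vocabulary of that kind of analysis. A latency is time elapsed since an event, and a factor needs levels. A meditation recording, as described, offers neither. The analyst would have to decide after data collection what to lock to, what to compare, or what to use in place of these measures.

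A second question arises only if a task with event markers exists but is not described. The windows then depend partly on inspecting the study's own waveforms. The plan does not say how far inspection may move a window from the prior-research one, whether waveforms are averaged over the arms first, or whether the person inspecting is blind to allocation. If windows follow the visible difference between arms, the group test no longer holds its nominal level.

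**Working it through.** **Step 1. Which recordings could carry the planned ANOVA?** The documents give no EEG figure to reproduce, so this step is a comparison of texts.

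| EEG source | Both arms? | Time zero described? | Linked to task condition? |
|---|---|---|---|
| Session meditation (summary) | Yes | No | No; one activity only |
| Home practice (summary, 3.1) | Headset given to mindfulness arm only | No | No |
| Calibration exercises (Section 6) | Not said to be done by controls | No | Nearest candidate for two levels, but not linked to the ANOVA; only stated use is the device algorithm |
| Biofeedback and graded sounds (Section 6) | Not stated for session recordings | No marker described; triggered by the EEG itself | No |

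The session meditation is the only source stated for both arms, and it has no described event. Home data cannot give a between-group contrast. Calibration could supply two levels if it were run and analysed in both arms, but it still supplies no time zero. Locking to biofeedback onsets would be circular, because the EEG being measured decides when they occur.

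**Step 2. How much could window choice matter if event-locked data exist?** From the documents: 50 per arm and 220 Hz sampling. Assumed: two-sided 5% level, a 100 ms window (22 samples; 22/220 s = 0.100 s), and no true group difference.

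A rough bound: with k independent candidate windows and the best one reported, the false-positive rate is 1 - 0.95^k.

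- k = 2: 1 - 0.9025 = 9.75%
- k = 3: 14.3%
- k = 5: 22.6%
- k = 10: 40.1%

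Neighbouring windows are correlated, so this was also simulated. Nine settings were used: epochs of 400, 600 or 800 ms crossed with noise smoothed at 40, 60 or 100 ms full width at half maximum. Each null trial was tested by a two-sample t-test on the window mean. The ranges run over the nine settings.

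| How the window is set | False positives |
|---|---|
| Fixed in advance, or at the maximum of the group-collapsed mean | about 4-7% |
| At each group's own visible component peak (assumed peak 1 SD, Gaussian SD 40 ms) | about 4-6% |
| Where arms differ most, centre within 25 ms of a published latency | about 8-13% |
| Same, within 50 ms | about 11-15% |
| Same, within 100 ms | about 17-24% |
| Same, anywhere in the epoch (worst case) | about 22-54% |

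With 1,500 trials per setting, the simulation standard error at 5% is sqrt(0.05 x 0.95 / 1500) = 0.56 percentage points. The first two rows are therefore compatible with 5%.

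**Step 3. What if the meditation EEG is simply cut into arbitrary epochs?** Assumed: group difference of 0.5 SD in log rhythm amplitude, 75 unlocked 800 ms epochs (75 x 0.8 s = 60 s), rhythm at 6, 10 or 20 Hz with random phase, 50 per arm.

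| Measure | Power |
|---|---|
| Mean of the signed average over epochs | 5-6% |
| Peak of that average | 9-29% |
| Rectified mean | 64-73% |
| Peak taken within each epoch | 64-73% |
| Log band power | 67-74% |

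The analysis can be run, but what it detects depends on an averaging order that the plan leaves open. Band power is not clearly better than rectified amplitude here.

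Steps 2 and 3 each test one two-group contrast, not the full factorial ANOVA.

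**The case against.** The best defence has four parts.

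1. **The gap may be one of description.** Section 6 does describe two calibration conditions and a discrete biofeedback response, and arbitrary epochs can always be cut. A reader might infer that a latency window is impossible here, or that task condition has no candidate at all. The documents do not support either inference. The supportable statement is that no event is specified, the candidates are not linked to the ANOVA, and the measures do not fit the recordings as described. Some pages are also absent from the public text, so absence can be claimed only for what is available.
2. **Visual inspection is ordinary practice.** It usually means finding a component, and the plan also cites prior research. A reader might infer that looking at waveforms by group inflates error in itself. Step 2 shows that it does not: windows at each group's own peak stay near 5%. The inflation comes from choosing by the group difference. The plan does not say it will do that, but it does not rule it out.
3. **The sizes are hypothetical.** This is correct. Apart from 50 per arm and 220 Hz, the simulation inputs are assumptions, and the window figures apply only if event-locked data exist.
4. **EEG is peripheral.** This is also correct. It is not among the constructs that Section 3.1 lists for the outcome measures, and the hypothesis in Section 2.2 concerns self-report and readiness for treatment.

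What stands is a stated method that does not match the described data, and a window rule without a safeguard. Parts 3 and 4 lower the priority.

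**Conclusion.** The point holds in a limited form. As documented, latency-window and peak measures with a task-condition factor do not fit the one kind of EEG described for both arms. If an event-related task exists, difference-guided window choice could raise a 5% error rate to roughly 8-13% with a tight limit around a published latency, and to 22-54% with none. The higher range is a worst case and not a forecast. These figures rest on the assumed window width, epochs and noise smoothness.

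A reader might infer that the trial's main conclusions are at risk. They are not: the symptom MANOVA, the mediation analysis and the latent difference score analysis do not use the EEG measures. Priority is low to moderate.

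**What to change.** **For the meditation recordings**, replace latency-window and peak measures with mean spectral power. Name the bands, electrodes and recording segment before any study EEG is examined, and keep them identical in both arms. The reason is that spectral power needs no time zero, not that it has more power.

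**If an event-related task is intended**, describe it, its event markers and the levels of task condition. Set the windows from prior research alone, or have an analyst blind to allocation set them on waveforms averaged over group and session.

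**In either case**, state that the group-by-session effect, or the baseline-adjusted group difference at week 8, is the EEG contrast that bears on treatment. Label the EEG analysis exploratory.

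**Cost.** This is plan wording only, provided raw session EEG is kept for both arms. The text mentions upload only of daily practice data, so retention must be confirmed; if session recordings are not kept, their export has to be set up. A task would need session time and event marking in both arms. The downside is less freedom to choose windows after seeing the data.
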